For all patients, 4 sets of blood samples (5 mL each) will be obtained via venipuncture or existing cannula access within a dosing interval. We propose to obtain 4 samples for each TDM in this study to generate more robust and accurate drug concentration-time curves for calculation of target attainment and to better characterise patients' pharmacokinetic profiles. For most patients (except those on intermittent extracorporeal therapies), blood samples will be obtained during end of infusion, 1 hour after infusion, 2 hours after infusion and within 30 minutes of the next scheduled dose (i.e. trough level) if beta-lactam is given as short infusion over \leq 30 minutes. If beta-lactam is given as extended infusion (e.g. 3-4 hours), blood samples will be obtained at mid-infusion, end of infusion, 1 hour after infusion and within 30 minutes of the next scheduled dose (i.e. trough level). For patients on intermittent extracorporeal therapies (e.g. intermittent dialysis), blood samples will be obtained at end of beta-lactam infusion, at the beginning of dialysis, end of dialysis and within 30 minutes of the next scheduled dose (i.e. trough level).

To ensure therapeutic targets are reached, further blood sampling, according to the schedule above, may be performed after dose adjustments or when there is a change in patient's clinical status (e.g. change in dialysis settings, change in renal function), which may warrant change in beta-lactam dosing regimen. Blood sampling for TDM will be stopped when beta-lactam has been discontinued, when therapeutic targets are achieved or when patient has been discharged from the hospital.

Assay of beta-lactam levels

All blood samples will be sent to our research laboratory for assay via liquid chromatographytandem mass spectrometry. All blood samples will be labelled by our study team using subject codes (no patient identifiers will be used).

Beta-lactam TDM and Dose Individualisation

The treating physicians will have the option to know the results of the TDM, once available. An infectious disease-trained pharmacist may make recommendations on dose adjustments based on the TDM results. However, accepting these recommendations will be at the discretion of the treating physicians.

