8.2. Statistical and Analytical Plans

Our primary outcome will be attainment of beta-lactam therapeutic targets: 100%fT>MIC, 40-70%fT>5xMIC, 100%fT>5xMIC. Proportion of patients, who achieve beta-lactam therapeutic targets, during the first and subsequent TDM will be determined. For the group of patients, who require dose adjustments, after the 1st TDM and need further TDM, the proportion of patients who require dose increment and dose reduction, the number of TDM performed to achieve therapeutic target and the mean/median time required to achieve therapeutic target will also be evaluated.

Correlation of primary outcomes will be made to the following secondary outcomes.

- a. Mortality at the end of therapy and within 30-day mortality.
- b. Days to defervescence
- c. Days to resolution of white blood cell count, pro-calcitonin and C-reactive protein.

Any incidence of adverse effects related to beta-lactam therapy will also be reported and evaluated in correlation to beta-lactam levels.

For univariate analyses with binomial outcomes (e.g. mortality), Chi-square test or Fisher's exact test will be performed where appropriate. For univariate analyses with time-dependent outcomes (e.g. days to defervescence, days to resolution of inflammatory markers), Kaplan-Meier analysis will be performed. For univariate analyses with continuous outcome variables (e.g. APACHE II score, SOFA score), Student's t-test and Mann-Whitney-U test will be performed for parametric and non-parametric data respectively. Multivariate analyses will then be performed to include potential confounders such as APACHE II score, SOFA score, Charlson comorbidity index, use of beta-lactam as culture-directed therapy, presence of multi-drug resistant infection, and presence of concurrent infections requiring additional antibiotics. Logistic regression will be used for binomial outcomes (mortality) while Cox regression will be used for time-dependent outcomes (days to defervescence, days to resolution of inflammatory markers).

To evaluate population pharmacokinetics in various patient groups, a specialised pharmacokinetic software will be used to develop population pharmacokinetic models. Model simulation will then be performed to design empiric dosing recommendations to guide local practice.

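### Section 8.2 relates efficacy outcomes only to target attained or not attained; a prespecified continuous-exposure analysis should be added beside that comparison

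*Combined protocol and SAP*

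**What the plan says.** Section 8.2 sets the exposure measure: "Our primary outcome will be attainment of beta-lactam therapeutic targets: 100%fT>MIC, 40-70%fT>5xMIC, 100%fT>5xMIC". It is summarised as a yes/no result per patient: "Proportion of patients, who achieve beta-lactam therapeutic targets, during the first and subsequent TDM will be determined". The link to efficacy follows: "Correlation of primary outcomes will be made to the following secondary outcomes", the list being mortality, days to defervescence, and days to resolution of white cell count, procalcitonin and C-reactive protein.

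The univariate methods are stated for binary outcomes ("For univariate analyses with binomial outcomes (e.g. mortality), Chi-square test or Fisher's exact test will be performed where appropriate") and for time outcomes ("For univariate analyses with time-dependent outcomes (e.g. days to defervescence, days to resolution of inflammatory markers), Kaplan-Meier analysis will be performed"). Both need exposure in groups. For the adjusted analyses, "Logistic regression will be used for binomial outcomes (mortality) while Cox regression will be used for time-dependent outcomes"; the section lists confounders but does not say how exposure enters these models.

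Two other statements bear on the point. Section 5 takes four samples per interval "to generate more robust and accurate drug concentration-time curves for calculation of target attainment". Section 8.2 treats harm differently: "Any incidence of adverse effects related to beta-lactam therapy will also be reported and evaluated in correlation to beta-lactam levels".

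**The concern.** Four concentrations over an interval give a trough, a trough/MIC ratio and the percentage of the interval above any chosen concentration. Once these are reduced to attained or not, a trough just under the MIC counts the same as one far below it, and one just above the same as one many times higher. If outcome improves gradually with exposure, that difference carries information which the split discards.

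Secondary objective 1 in Section 2 (relating achieved targets to clinical outcomes) is where the study can least afford this. Section 8.1 sets the size by assay budget, with no power calculation, and deaths will be a fraction of about 80 patients. Section 1 also says that no target has been extensively validated clinically and that the candidates have not been compared on outcome. Whether risk changes sharply at a target is therefore an open question, and yes/no coding alone cannot answer it.

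**Working it through.** **The plan's own figure.** 40,000/125 = 320 assays and 320/4 = 80 patients, which agrees with Section 8.1. Repeat TDM draws on the same assays. If a share f of patients has a second full set, n = 320/[4(1+f)]: 80 at f = 0, 64 at 0.25, 53 at 0.5 and 40 at 1. Incomplete sets could raise n, since recruitment runs until 320 assays are done.

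**Anticipated attainment.** Section 2 hypothesises suboptimal dosing in at least half of patients, so at most 50% attain. Section 1 cites failure in at least 35-50%, so at most 50-65% attain. Both are ceilings. The documents give no separate figure for the strictest target.

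**Information kept by a yes/no split.** For a normal exposure with a linear effect and a share p attaining, relative efficiency = φ(z_p)²/[p(1−p)], where z_p is the normal quantile and φ the normal density.

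| Attaining | φ(z_p) | Efficiency | Loss | 80 patients act like |
|---|---|---|---|---|
| 50% | 0.399 | 0.159/0.2500 = 0.637 | 36% | 51 |
| 65% (or 35%) | 0.370 | 0.137/0.2275 = 0.603 | 40% | 48 |
| 20% (or 80%) | 0.280 | 0.0784/0.16 = 0.490 | 51% | 39 |
| 10% (or 90%) | 0.175 | 0.0308/0.09 = 0.342 | 66% | 27 |

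The last two rows are sensitivity values with no source in the documents.

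**Other shapes.** For a uniform exposure the efficiency is 3p(1−p): 0.75 at 50% and 0.68 at 35% or 65%, so the loss is 25-32%. If the three targets were used jointly as four ordered groups, efficiency was 0.77-0.86 for the cut-points tried, a loss of 14-23%.

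**Power.** The documents give no mortality rate, effect size or alpha; these are assumptions. All runs use n = 80 and two-sided 5%.

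- 20% mortality, odds ratio 0.5 per SD, linear, half attaining: about 65% with continuous exposure (likelihood-ratio test) and about 46% with the yes/no variable (chi-square or Fisher).
- Likelihood-ratio test on both sides, 20% risk at mean exposure, same effect size: 68-70% continuous, against 50%, 49% and 46% at 50%, 65% and 80% attainment. At 30% risk: 77-79% against 59%, 58% and 52%.
- True step at the target, half attaining: 62% continuous against 79% yes/no (30% risk, odds ratio 4), and about 45-47% against 62-65% (20% mortality, odds ratio 0.25). The ordering reverses.

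**Can one continuous index separate the targets?** log2(trough/5×MIC) = log2(trough/MIC) − log2 5 = log2(trough/MIC) − 2.32. A constant shift leaves slope and p-value unchanged, so a linear term alone cannot tell 100%fT>MIC from 100%fT>5xMIC. The yes/no comparison or the shape of a fitted curve is needed for that.

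**The case against.** The strongest reply is that thresholds are the research question. Section 1 sets out to find which target is best for practice, and secondary objective 1 names achieved targets as the exposure. That stands: a reader might infer that attainment is the wrong exposure and should be replaced, but the documents make comparing targets an aim, and a linear log2(trough/MIC) term cannot separate two of the three. If risk does step at a target, the yes/no variable is also the more powerful one.

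Second, the ratio is not always fully measured. Section 5 assumes the highest susceptible CLSI MIC for dose recommendations when none is available. If the same value is used for attainment, the denominator is assumed for an unknown share of patients. This also stands, and it affects attainment as well.

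Third, a much larger power gap can be produced, about 65% against 22% with a quarter attaining. A reader might attribute all of it to dichotomising. Part comes from changing to Fisher's test: with the likelihood-ratio test on both sides the yes/no figure is about 37%.

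Fourth, this is a secondary objective in an observational feasibility study that makes no power claim. That limits how serious the gap is. It does not remove the case for a low-cost addition that uses data already collected.

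**Conclusion.** The point holds as a gap in the efficacy exposure-outcome analyses. Section 8.2 specifies no continuous-exposure analysis for mortality, defervescence or marker resolution, though the sampling supports one.

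Under a roughly normal exposure and a linear effect, the loss is about 36-40% at 50-65% attainment. It reaches about half only near 20%, which is possible for the strictest target but is not stated. A flat claim that a third to a half of the information is discarded is not supported, since the loss depends on the distribution of exposure and can reverse under a threshold effect. Nor can one say that every exposure-outcome analysis is dichotomised: adverse effects are evaluated against levels, and the regression coding is silent. The sample is about 80 with one full set each and fewer with repeat TDM; 80 is not a strict maximum.

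This is worth correcting before analysis. It does not undermine the primary outcome.

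**What to change.** In Section 8.2:

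1. Keep the attainment proportions as the primary outcome, and keep the yes/no comparison of the three targets with outcome. State how exposure is coded in the logistic and Cox models.
2. For each efficacy outcome, add a prespecified continuous-exposure analysis to those models: log2(trough/MIC) from the first TDM, with one non-linear term. The first TDM gives one value per patient before any TDM-guided dose change.
3. Use the fitted curve, with its confidence band, to judge whether risk changes near 1×MIC or 5×MIC.
4. If %fT>5xMIC is also used, allow for its bounds at 0 and 100%.
5. Repeat the analysis in patients with a measured MIC.

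The cost is wording and one extra model per outcome, with no new samples or data. The drawbacks are a linearity assumption to check and an effect per doubling that clinicians will find less familiar. With few deaths (80 × 0.20 = 16 under the assumed 20% mortality), the non-linear term will be imprecise and the curve should be read descriptively.

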Optimal treatment for resistant bacterial infections is limited. Currently available alternative antibiotics, such as tigecycline, polymyxin B and aminoglycosides, are often associated with adverse effects such as hepatotoxicity and nephrotoxicity. In addition, pathogens with multidrug resistance could already be resistant to these agents [19]. Unfortunately, very few novel antibiotics are available in the pipeline and for the newly approved agents (e.g. ceftolazone/tazobactam), resistance is already being reported [20]. These novel agents are also significantly costlier than currently available antibiotics. In such desperate situations, prescribers may need to resort to high dose beta-lactam therapy, often exceeding current licensed recommendations, to achieve beta-lactam levels beyond the elevated minimum inhibitory concentrations (MIC) of the resistant pathogens to ensure maximum bacterial kill and efficacy [3,21]. This implies that doses of beta-lactams used would be at or near the threshold for adverse effects or toxicity and the concept of wide therapeutic window for beta-lactams no longer applies. In order to balance between efficacy and toxicity in such setting, beta-lactam TDM with subsequent dose adjustment would be required to ensure optimal therapy. This will also give prescribers confidence to use such high dose beta-lactam regimens.

2. Use of high dose beta-lactam therapy to treat pathogens with "intermediate" susceptibility

The Clinical and Laboratory Standards Institute (CLSI) and the European Committee on Antimicrobial Susceptibility Testing (EUCAST) are shifting towards reclassifying pathogens with intermediate beta-lactam susceptibility to susceptible-dose-dependent (SDD) or susceptible, increased exposure, respectively [22,23]. This implies that high dose beta-lactam therapy can still be used to treat pathogens with "intermediate" beta-lactam susceptibility. Only beta-lactam TDM will enable us to ensure that the high dose beta-lactams dosage regimens are sufficient for such infections while avoiding risks for toxicity. If high dose beta-lactam therapy

could be used with confidence in these situations, we can avoid unnecessary switch to other agents, which may be more broad-spectrum, toxic or expensive. This will allow us to reserve the use of these antibiotics for highly resistant pathogens.

3. Use of pharmacokinetic/pharmacodynamics-guided approach to individualise and optimise beta-lactam therapy

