5. STUDY DESIGN AND PROCEDURES/METHODOLOGY

This is a prospective observational study conducted in Singapore General Hospital from October 2019 to September 2020. Patients will be screened for eligibility using criteria 4.3 and 4.4. If women of childbearing age are eligible, the beta HCG result taken during the potential subject's course of hospitalisation will be used to exclude pregnant women. If no beta HCG result is available, clinical case notes will be referred to confirm non-pregnancy status.

Eligible patients will be approached by their treating physicians to seek their consent to be referred to the study team. Informed consent will be taken directly from the patient by the study team once patient is agreeable to be referred to the study team. For subjects who do not have the mental capacity to exercise rational judgement, primary physician will assess and document their mental capacity using the Documentation of Capacity form and substituted consent will be obtained by the study team from the spouse, parent, guardian, or legally acceptable representative of the subject. Consent for continued participation will be obtained from patient directly when he regains mental capacity to give informed consent.

Blood sampling and data collection will only commence once informed consent has been taken. Subjects may withdraw voluntarily from participation in the study at any time. Once they have withdrawn from the study, all subsequent blood sampling and data collection will be discontinued.

All patients will be followed up until end of beta-lactam therapy, 30 days from commencement of beta-lactam therapy, hospital discharge or mortality, whichever occurs later.

Blood sampling:

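### End-of-therapy mortality has an undefined window that varies by patient but is analysed as a plain binary outcome, so its association with target attainment can be distorted in either direction

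*Combined protocol and SAP*

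**What the plan says.** Section 8.2 takes attainment of three pharmacokinetic/pharmacodynamic targets as the primary outcome and then states: "Correlation of primary outcomes will be made to the following secondary outcomes". The first item listed is "Mortality at the end of therapy and within 30-day mortality". One line therefore holds two mortality outcomes, one with a fixed horizon and one without.

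The analysis is binary for mortality only: "Logistic regression will be used for binomial outcomes (mortality) while Cox regression will be used for time-dependent outcomes". Univariate mortality comparisons use chi-square or Fisher's exact test. Kaplan-Meier and Cox methods are kept for defervescence and inflammatory markers. On adjustment, 8.2 says "Multivariate analyses will then be performed to include potential confounders such as APACHE II score, SOFA score, Charlson comorbidity index", followed by culture-directed use, multidrug-resistant infection and concurrent infection. Therapy duration is not named, although the list is given only as examples.

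Section 8.2 does not define the end of therapy. The opening part of section 5 says "All patients will be followed up until end of beta-lactam therapy" and then lists further milestones, taking the latest of them and counting its 30 days from the start of the beta-lactam. The Data Collection part of section 5 counts from study entry and takes the earliest of 30 days, discharge or death.

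On knowledge of the level, section 5 says: "The treating physicians will have the option to know the results of the TDM, once available". Acting on any dose recommendation is left to the physician.

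**The concern.** A binary comparison of deaths is fair only if both groups are observed for comparable periods. Here each patient's period ends when therapy ends. That date is a clinical decision, possibly made with the exposure (the level) in view, and may also reflect the patient's progress. Eligibility runs from suspected infection to deep-seated and resistant infection, so course lengths can be expected to vary widely.

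There is a second link between exposure and window. Attainment is assessed at the first and at later rounds of monitoring, and sampling ceases once the beta-lactam is stopped. A patient below target at the first round can be reclassified as attaining only by remaining on the drug. If later attainment enters the correlation, attainment and length of therapy are tied together by the design.

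At stake is part of secondary objective 1, which relates the achieved targets to clinical outcomes, and the aim stated in section 1 of finding which target is best for practice. Neither mortality outcome has priority over the other, so an association produced by unequal windows could be reported as evidence on that question.

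**Working it through.** **The plan's own figures.** Sections 4.1 and 8.1 give a budget of 40,000 and a cost of 125 per assay. 40,000 / 125 = 320 assays, and 320 / 4 = 80 patients. Both reproduce. The documents give no mortality rate, course length, power or effect size, so the inputs below are assumptions.

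**Assumptions.** The hazard of death is constant and equal in both groups (no effect of attainment). 30-day mortality m is 20%, varied from 10% to 30%. All patients in a group have the same course length T.

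**Formulas.**
- h = −ln(1 − m) / 30. For m = 0.20, h = 0.2231 / 30 = 0.00744 per day.
- Risk of death by end of therapy = 1 − exp(−hT).
- Odds ratio (OR) = odds of death in attainers / odds of death in non-attainers, which is what logistic regression estimates.

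**Results with no true effect, m = 20%.**

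| Assumed pattern | T, attainers | T, non-attainers | Risk, attainers | Risk, non-attainers | OR |
|---|---|---|---|---|---|
| Equal windows | 10 | 10 | 7.2% | 7.2% | 1.00 |
| Non-attainers stop much earlier | 10 | 4 | 7.2% | 2.9% | 2.56 |
| Non-attainers stop somewhat earlier | 10 | 7 | 7.2% | 5.1% | 1.44 |
| Attainers finish earlier | 7 | 14 | 5.1% | 9.9% | 0.49 |
| Non-attainers kept on longer | 10 | 14 | 7.2% | 9.9% | 0.70 |

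The mortality assumption hardly matters. For m from 10% to 30%, the second row gives 2.53 to 2.59, the fourth 0.48 to 0.49 and the fifth 0.70 to 0.71. Course length drives the result.

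**Results with a true hazard ratio of 0.5 favouring attainment, m = 20% in non-attainers.**
- Equal 10-day windows: 3.7% against 7.2%, OR 0.49.
- Attainers 10 days, non-attainers 4: 3.7% against 2.9%, OR 1.25. The sign is reversed.
- Attainers 7 days, non-attainers 14: 2.6% against 9.9%, OR 0.24. The benefit is exaggerated.
- Fixed 30 days for all: attainer risk = 1 − √0.80 = 10.6%, against 20%. OR = (0.1056 / 0.8944) / (0.20 / 0.80) = 0.47, with no distortion from the window.

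**Scale in this study.** If about 80 patients split evenly (an assumption), the second row of the table implies 40 × 0.072 = 2.9 expected deaths among attainers and 40 × 0.029 = 1.2 among non-attainers.

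**The case against.** The strongest reply is that the plan already contains the remedy. 30-day mortality stands in the same line, is analysed against attainment by the same methods, and does not depend on when therapy stops. Both mortality outcomes are secondary, and objective 1 also covers clinical response and microbial eradication. This stands, and it limits the impact. It would be too much to say that objective 1 as a whole is undermined.

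A reader might infer that the bias runs against attainment, because sub-target patients would be switched away sooner. The documents do not support that. Section 5 provides for dose recommendations and repeat sampling after a low level and gives no rule for stopping by level. The remark in section 1 that "we can avoid unnecessary switch to other agents" concerns pathogens of intermediate susceptibility and expects fewer switches when monitoring supports high-dose therapy. It does not say that a low level brings an earlier one.

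A reader might also infer that a death after a switch to another antibiotic is certainly not counted. That is one possible reading. Section 8.2 leaves the end of therapy undefined, and the end of the beta-lactam appears only as one of several follow-up milestones in section 5.

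Finally, the course lengths in the working are chosen, and the wider contrasts are strong ones. Milder contrasts (7 against 10 days) give an OR of about 1.4, or about 0.7 if reversed. With so few expected deaths, such a distortion would be hard to tell from chance. This weakens any claim about size. It does not make the comparison valid, and a bias of unknown sign cannot be allowed for at interpretation.

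**Conclusion.** The point holds in limited form. As written, 8.2 correlates attainment with a mortality outcome whose window is undefined, varies by patient and depends on discretionary decisions of physicians who may know the level, and it makes no allowance for time at risk. The association can be distorted in either direction with no effect on death: odds ratios from about 0.5 to 2.6 in the illustration, against 1.0 with a common window. Those figures rest on an assumed constant hazard, assumed 30-day mortality and assumed course lengths, and show possible size only. No direction can be claimed from the documents.

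The damage is confined to one of two secondary mortality outcomes; the primary outcome is untouched. The other mortality outcome is a safe replacement only if 30-day status is actually obtained, and the two follow-up statements in section 5 disagree on that. Under the Data Collection rule, follow-up can end at discharge, and the window would again vary by clinical decision. The change should be made, because it is cheap and the comparison is otherwise uninterpretable.

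**What to change.** - **Section 8.2, mortality outcome.** Make death within 30 days of a stated time zero the only mortality outcome correlated with target attainment. State that time zero explicitly, since section 5 currently uses both the start of the beta-lactam and study entry.
- **Section 8.2, end of therapy.** Keep end-of-therapy mortality as a description only. Define the end of therapy, including whether a change to another antibiotic for the same infection closes the window. Tabulate the reason for stopping the beta-lactam (completed, switched, adverse effect, death) by attainment group.
- **Section 5.** Reconcile the two follow-up rules (the latest milestone in the opening part, the earliest under Data Collection) and their different starting points, so that 30-day vital status is obtained for every patient, including after discharge.

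The cost is a few sentences, one additional data field for the reason for stopping, and one fewer correlated mortality outcome. Regimen changes and concurrent antibiotics are already collected. Checking status after discharge is extra work only relative to the Data Collection rule; the opening part of section 5 already implies it.

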4.3. Inclusion Criteria

- a) Age ≥ 21 years old
- b) Admitted to Singapore General Hospital
- c) Receiving beta-lactams for documented or suspected infection
- d) With indication for beta-lactam TDM: critically ill, altered pharmacokinetics (burns, obese, on extracorporeal therapy e.g. dialysis), immunocompromised (haematology/oncology patients), resistant pathogens, deep-seated infections, suspected

or at risk for adverse effects

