The infectious disease trained pharmacist may use pharmacokinetic software to analyse drug concentration-time profile to guide dose adjustments. If available, dose recommendations will be based on the MIC of the known pathogen, which will be provided by the local microbiology laboratory. Where no pathogen was formally identified, MICs are not available or cultures are pending, the highest MIC (according to the Clinical and Laboratory Standards Institute (CLSI criteria) for susceptible bacteria to the antibiotic will be assumed.

Data Collection

All patients will be followed up from study entry to 30 days from study entry, hospital discharge or mortality, whichever occurs earlier.

Data will be collected from electronic medical records, using a standardised data collection form. These will include:

•patient demographics (unique identifier, age, gender, race, body weight, height, comorbidities including Charlson Comorbidity Index)

•pharmacokinetic-specific data (use of extracorporeal therapy/dialysis and settings, urine output, serum creatinine, albumin)

•clinical data (temperature, blood pressure, heart rate, respiratory rate, mortality, cause of mortality, severity of illness indicators such as APACHE II score and SOFA score, incidence of beta-lactam-related adverse events/side effects as reported by primary physicians, admission and discharge date from hospital and from intensive care unit if applicable)

•laboratory data (albumin, serum creatinine, procalcitonin, CRP, total white count)

•infection-related data (site and type of infection, pathogens isolated and their susceptibility results and reported minimum inhibitory concentrations)

•drug-related data (beta-lactam dosing regimens including any change to dosing regimens, concurrent antibiotic use history and their dosing regimens, presence of any drug which may interact with beta-lactams or interfere with beta-lactam assay results)

•beta-lactam assays levels, attainment of therapeutic targets and whether dose adjustments were made

Data will be stored in a password-protected database and only study team members will have access to data. Identifiers will be stored separately from collected data. Data collection forms will not contain identifiers (e.g. NRIC, name, date of birth). All hardcopy data collection forms and consent forms will be stored under lock and key in the cupboard at [name] of

Pharmacy department in Singapore General Hospital.

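### Days to resolution of white cell count, procalcitonin and CRP rests on unscheduled routine tests, so Kaplan-Meier medians run late and the Cox comparison by target attainment is open to bias

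*Combined protocol and SAP*

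**What the plan says.** Section 8.2 (Statistical and Analytical Plans) names "Days to resolution of white blood cell count, pro-calcitonin and C-reactive protein" among the secondary outcomes that are to be correlated with target attainment. The univariate method is given as "For univariate analyses with time-dependent outcomes (e.g. days to defervescence, days to resolution of inflammatory markers), Kaplan-Meier analysis will be performed". For the multivariable step, "Cox regression will be used for time-dependent outcomes (days to defervescence, days to resolution of inflammatory markers". Adjustment is for "potential confounders such as APACHE II score, SOFA score, Charlson comorbidity index, use of beta-lactam as culture-directed therapy" and further infection-related factors. Care setting and test frequency are not in that list, although it is worded as open.

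The marker values come from section 5, Data Collection: "Data will be collected from electronic medical records, using a standardised data collection form". The items to extract include "laboratory data (albumin, serum creatinine, procalcitonin, CRP, total white count", with no days or frequency attached. The only blood draws the study schedules are the four per dosing interval for drug levels, and of these section 5 says "All blood samples will be sent to our research laboratory for assay via liquid chromatographytandem mass spectrometry".

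Neither section defines resolution, says how to handle a marker that is normal or missing at baseline, gives a censoring rule, or mentions interval censoring.

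**The concern.** A marker cannot be seen to resolve until someone tests it. With routine testing, the recorded date is the first qualifying result on or after the true date, and the delay depends on the gap between tests. Kaplan-Meier and Cox, used in their ordinary form on that date, take it as the event time.

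Two consequences follow. First, the reported medians run late whatever the exposure. Second, if the gap differs between attainers and non-attainers, the hazard ratio picks up the difference in testing as well as any difference in recovery.

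The documents make such a difference plausible:
- Section 4.3 enrols a mixed population: "critically ill, altered pharmacokinetics (burns, obese, on extracorporeal therapy e.g. dialysis), immunocompromised (haematology/oncology patients", among others.
- Section 1 says pharmacokinetics are variable and unpredictable in several of these groups, so care setting may be tied to attainment. It may also be tied to how often blood is tested.
- Section 5 lets treating physicians see the drug-monitoring result, so ordering of tests could respond to attainment directly.

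Section 1 says the study is meant to determine which target is optimal for practice, and these outcomes feed that comparison.

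**Working it through.** **Plan's own figures.** Section 8.1: 40,000/125 = 320 assays and 320/4 = 80 patients. Both reproduce. No power, effect size or event count is stated for any outcome.

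**Assumptions, because the documents give none of these.** True median 5 days (7 as a second case), test gaps of 1 to 5 days, and 80 patients split 40/40.

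**Step 1: delay in the median.** Take exponential resolution times with λ = ln 2/5 = 0.1386 per day and tests every g days at a random phase. At time t the last test was U days ago, with U uniform on (0, g). The event is still unrecorded if true resolution came after t − U. Averaging over U, for t ≥ g:

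S_obs(t) = e^(−λt) × m(g), where m(g) = (e^(λg) − 1)/(λg)

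Observed median = 5 + ln m(g)/λ

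| Gap g (days) | m(g) | Observed median (days) |
|---|---|---|
| 1 | 1.0726 | 5.51 |
| 2 | 1.1524 | 6.02 |
| 3 | 1.2400 | 6.55 |
| 4 | 1.3365 | 7.09 |

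If the two attainment groups are completely separated by schedule, the spurious differences are:
- 1 vs 3 days: 6.55 − 5.51 = about 1.0 day
- 1 vs 2 days: 6.02 − 5.51 = about 0.5 day
- 2 vs 4 days: 7.09 − 6.02 = about 1.1 days

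Simulation of 400,000 patients per scenario agrees: 5.47 vs 6.52, 5.52 vs 6.04 and 6.03 vs 7.11.

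**Step 2: overlapping groups.** Suppose 30% of one group and 70% of the other are tested every 3 days, and the rest daily. The multipliers are averaged:
- 0.7 × 1.0726 + 0.3 × 1.2400 = 1.123, median 5.84
- 0.3 × 1.0726 + 0.7 × 1.2400 = 1.190, median 6.25

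The difference is about 0.4 day. The same sum gives 0.6 day for a 20/80 mix and 0.2 day for 40/60.

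**Step 3: Cox hazard ratio, no true effect.** Simulation of 40 vs 40 with Weibull times (shape 1.5), dates rounded up to whole days, censoring at day 30, Efron ties and a two-sided 5% Wald test. The first group is the one tested more often. 1000 replicates, except 600 for the mixes.

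| Gaps (days) | HR (rejection), median 5 | HR (rejection), median 7 |
|---|---|---|
| 1 vs 1 | 1.00 (7.3%) | 1.01 (5.3%) |
| 3 vs 3 | 1.00 (4.9%) | 1.00 (3.5%) |
| 1 vs 2 | 0.88 (8.8%) | 0.93 (7.1%) |
| 1 vs 3 | 0.80 (17.0%) | 0.86 (10.8%) |
| 2 vs 4 | 0.80 (16.9%) | 0.85 (11.2%) |
| 1 vs 5 | 0.65 (47.3%) | 0.72 (28.1%) |
| 1 and 3, 30/70 mix | 0.91 (5.7%) | not run |
| 1 and 3, 40/60 mix | 0.95 (5.3%) | not run |

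A separate run of the 30/70 mix gave 0.90. Equal gaps leave the hazard ratio at 1.00 to 1.01, although the recorded median is still about 6 days (daily) or 7 days (every 3 days) against a true 5.

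With a true hazard ratio of 1.5 and a median of 5 days, a common schedule gives 1.52 (daily) or 1.48 (every 3 days). Daily against 3-day testing gives 1.17 if the faster-resolving group is tested less often and 1.95 if it is tested more often.

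**Step 4: does interval censoring help?** An interval-censored Weibull model under the same assumptions (600 replicates) gave null hazard ratios of 1.01, 1.00 and 1.01 for gaps 1 vs 3, 2 vs 4 and 1 vs 5. Exact dating gave 0.81, 0.80 and 0.64. A true 1.5 came back as 1.50 and 1.49. The spread of the log hazard ratio was about 0.24, against 0.25 for exact dating. This check favours the method: the data were Weibull and test timing was unrelated to recovery.

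**The case against.** A reader might infer that the planned comparison is biased. The documents do not support that. They give no testing frequency for any ward, and Step 3 shows no hazard-ratio bias when gaps are equal. The link from setting to attainment has some support in section 1; the link from setting to testing is inference. This objection stands, and it is why the point is put as open to bias.

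The 1.0-day figure needs every patient in one attainment group to be on one schedule and every patient in the other group on another. Real groups would overlap. With a 30/70 mix the rejection rate of 5.7% lies within the 3.5% to 7.3% seen with equal gaps. This also stands, so 1.0 day is the complete-separation case and not an expected value.

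Three other strong readings fail:
- That untested patients remain at risk to the end of follow-up. Section 8.2 states no censoring rule; this would be a guess from the names of the methods.
- That patients never retested add error in the same direction. The direction depends on which attainment group they fall in, and the simulations did not model them.
- That covariate adjustment does nothing. If testing follows severity, APACHE II and SOFA may absorb part of the difference, and the covariate list is open. They still cannot re-date an event.

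Finally, standard interval-censored methods assume that test timing is uninformative, whereas the concern is partly that testing follows clinical state. That limits what the remedy can promise but does not favour the current plan, which makes no allowance for test timing.

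**Conclusion.** The point holds in a limited form. The late-running medians follow directly from unscheduled testing: by about 0.5 day with daily tests and 1.6 days with 3-day tests in Step 1. Bias in the Cox comparison is conditional on testing frequency differing by attainment. Its size and direction cannot be fixed from the documents. Under the assumed gaps with a true median of 5 days, it ranges from a hazard ratio near 0.95 (40/60 mix) through about 0.90 (30/70) to 0.80 (complete separation, daily vs 3-day) and 0.65 (daily vs 5-day). With a true median of 7 days the completely separated cases are milder.

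The change should be made, because it is cheap and the plan has nothing in its place. It concerns one group of secondary outcomes in a study of about 80 patients. Primary target attainment is untouched.

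**What to change.** In section 8.2:
1. Define resolution for each marker, including whether a low white cell count counts as abnormal (section 1 names febrile neutropaenia), and restrict each analysis to patients abnormal at baseline.
2. Record the dates of the last abnormal and the first resolved result.
3. Replace Kaplan-Meier and Cox on the first normal date with a Turnbull estimate and an interval-censored Weibull or proportional-hazards model.
4. Censor each marker at its own last test.
5. Report test frequency by attainment group, so that readers can see whether it differed.
6. Report a marker descriptively where serial values are sparse.
7. State that the method assumes test timing is uninformative given the covariates. It reduces the bias but does not guarantee its removal.

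In section 5, reconcile the two follow-up statements. The design text runs to the latest of its listed events; Data Collection stops at the earliest. They also count 30 days from different starting points (start of beta-lactam therapy, and study entry). Both differences affect censoring.

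The cost is SAP wording and two dates per marker from records already being reviewed, with no extra blood tests. Intervals may be somewhat wider, although the simulation showed no visible loss of precision, and procalcitonin and CRP may end up descriptive only.
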